APPENDIX III: DEFINING EXPECTED OUTCOMES

III.1 BACKGROUND

A literature search and review were conducted to better define expected primary endpoint outcomes for this study.

III.2 SEARCH CRITERIA AND METHODS

Expected outcomes for the primary safety endpoint and the primary performance endpoint are based on a systematic search and review of the literature on Abbott Mechanical Heart Valve surgeries indexed in the US National Library of Medicine's PubMed database.

III.3 SEARCH AND REVIEW RESULTS

11. **What is the primary purpose of the *Journal of Clinical Endocrinology and Metabolism*?**

[figure not shown]
III.4 EXPECTED OUTCOMES

100% of the time, the system is able to correctly identify the target class. This is a significant improvement over the baseline model, which only achieves 50% accuracy. The results are summarized in the following table:

Clinical Investigation Plan

III.5 LITERATURE DATA SUMMARY TABLES

Table 3. MHV Studies [REDACTED]

Clinical Investigation Plan

Clinical Investigation Plan

APPENDIX V: RATES OF FORSEEABLE ADVERSE EVENTS

Clinical Investigation Plan

Clinical Investigation Plan

APPENDIX VI: CASE REPORT FORMS

Case report forms will be provided under a separate cover.

Clinical Investigation Plan

APPENDIX VII: INFORMED CONSENT FORM

Informed Consent Form (ICF) templates will be provided under a separate cover.

Clinical Investigation Plan

APPENDIX VIII: MONITORING PLAN

A copy of the Monitoring Plan can be obtained upon request from the Sponsor Clinical Project Manager for the clinical investigation.

Clinical Investigation Plan

[figure not shown]
APPENDIX IX: REVISION HISTORY

This CIP may be amended as appropriate by the Sponsor. Rationale will be included with each amended version in the revision history table below. The version number and date of amendments will be documented.

IRB/EC and relevant Regulatory Authorities, if applicable, will be notified of amendments to the CIP.

Amendment Number	Version	Date	Details	Rationale

Clinical Investigation Plan

Clinical Investigation Plan

APPENDIX X: CIP SUMMARY

Clinical Investigation Name and Number	RC-PMCF
Title	Regent China Post-Market Clinical Follow-up Study
Objective	Confirm the long-term safety and performance of Abbott Medical's Regent, model AGN-751 and AGFN-756, for replacement of native or prosthetic aortic valves.
Device Under Investigation	Abbott Medical's Regent Mechanical Heart Valve
Number of Subjects Required for Inclusion in Clinical Investigation	200
Clinical Investigation Design	Prospective, non-randomized, observational, multi-center study
Primary Endpoints	The primary safety endpoint is freedom from valve-related mortality at 5 years. The primary performance endpoint is freedom from valve-related reoperation at 5 years.
Subject Follow-up	Baseline, implant, discharge, 3-months, 6-months, and annually post-implant
Inclusion Criteria	
 1. Patient is eligible to be implanted with Regent to replace a native or prosthetic aortic valve per Regent MHV's IFU 2. Subject will be ≥ 18 years of age at time of being consented 3. Subject, provides written informed consent prior to any clinical investigation-specific procedure.
Exclusion Criteria	
 1. Subject is unable to tolerate anticoagulation therapy 2. Subject has active endocarditis 3. Subject is currently participating in another clinical investigation which may interfere with the effectiveness of anticoagulation therapy

Clinical Investigation Plan

	
4. Pregnant or nursing subjects and those who plan pregnancy during the clinical investigation follow-up period. Women of child-bearing potential must have a documented negative pregnancy test within one week prior to enrollment5. Subject has anomalous anatomy or medical, surgical, psychological or social history or conditions that, in the Investigator's opinion, could limit the subject's ability to participate in the clinical investigation or to comply with follow-up requirements of the clinical investigation results6. Subject is unable to read or write or has a mental illness or disability that impairs their ability to provide written informed consent7. Subject's life expectancy is less than 1 year in the opinion of the Investigator
--	---

## Statistical Analysis Plan

### 1.0 SYNOPSIS OF STUDY DESIGN

#### 1.1 Purpose of the Statistical Analysis Plan

This statistical analysis plan (SAP) is intended to provide a detailed and comprehensive description of the planned methodology and analysis to be used for ABT-CIP-10412, the Regent China PMCF clinical investigation. This plan is based on the Version C of Clinical Investigation Plan.

#### 1.2 Clinical Investigation Objectives

The objective of this clinical investigation is to confirm the long-term safety and performance of Abbott Medical's Regent, model AGN-751 and AGFN-756, for replacement of native or prosthetic aortic valves in a Chinese population.

#### 1.3 Clinical Investigation Design

The RC-PMCF is designed to meet the PMCF requirements of the NMPA. This is a prospective, observational, multi-center study of subjects clinically indicated for implantation of an Abbott Medical's Regent Valve. Two hundred subjects will be enrolled into the study, that undergo surgical aortic valve replacement using a commercially available Regent valve.

Study enrollment will occur at up to 10 centers in China. The study will enroll subjects expected to be implanted with an Abbott Regent Valve who meet all study eligibility requirements. Additionally, subjects who do enroll and do not undergo the Regent MHV implant within 60 days of enrollment will be withdrawn from the study and will not contribute to the study sample size.

Subjects will be followed for 5 years post-implant; the expected duration of enrollment is [REDACTED]. Study visits or data collection will occur at baseline, implant, discharge, 3 months, 6 months, and annually through 5 years post-implant.

#### 1.4 Endpoints

##### 1.4.1 Primary Safety Endpoint

The primary safety endpoint is freedom from valve-related mortality at 5 years.

##### 1.4.2 Primary Performance Endpoint

The primary performance endpoint is freedom from valve-related reoperation at 5 years.

##### 1.4.3 Descriptive Endpoints

The following outcomes will be assessed as descriptive endpoints for the study:

- Annualized rate from the following events from implant through five years post-implant:
  - All-cause mortality
  - Reintervention
  - Major bleeding

## Statistical Analysis Plan

- Thromboembolism
- Valve thrombosis
- Endocarditis (Operated Valve)
- Major Paravalvular Leak

- NYHA (New York Heart Association) Functional Class at baseline and annually post-implant

### 2.0 ANALYSIS CONSIDERATIONS

#### 2.1 Analysis Populations

##### 2.1.1 Implant Population

#### 2.2 Statistical Methods

##### 2.2.1 Descriptive Statistics for Continuous Variables

For continuous variables (e.g., age, weight, height, etc.), results will be summarized with the numbers of observations, means, and standard deviations, with quartiles, minimums, maximums, and 95% confidence intervals, where specified.

##### 2.2.2 Descriptive Statistics for Categorical Variables

For categorical variables (e.g. gender, diabetic status, etc.), results will be summarized with subject counts and percentages/rates,

##### 2.2.3 Survival Analyses

Survival analysis will be conducted to analyze time-to-event variables. Subjects without events will be censored at their last known event-free time point.

##### 2.2.4 Analysis in Response to COVID-19 Impact

As the Coronavirus Disease 2019 (COVID-19) pandemic has spread around the globe, the following analysis mechanism will be implemented to minimize the potential confounding effect from this emerging infectious disease for the trial primary and secondary endpoints set forth in assessing the trial success and labeling claims. In alignment with the EU guidance document “Guidance on the Management of Clinical Trials during the COVID-19 (Coronavirus) Pandemic” updated on 28-April-2020, additional consideration was given to the impact of the COVID-19 pandemic on the primary endpoint analyses for this study. As such, prespecified methods are included in the sections that follow to indicate the handling of any outcomes impacted by COVID-19 as well as efforts to minimize missing endpoint data during the COVID-19 pandemic. Specific analyses to address COVID-19 impacts are included in relevant

## Statistical Analysis Plan

subsections in Section 2.10.

### 2.3 Endpoint Analysis

#### 2.3.1 Primary Endpoint(s)

The primary safety endpoint is freedom from valve-related mortality

The primary performance endpoint is freedom from valve-related reoperation.

#### 2.3.2 Secondary Endpoints

No secondary endpoints are specified for this study.

### 2.4 Sample Size Calculations

Two hundred implanted subjects will be enrolled.

### 2.5 Interim Analysis

No formal interim analyses are planned for this study. As such, no formal statistical rule for early termination of the trial is defined. Interim study reports with descriptive analysis may be produced for regulatory or reimbursement purposes.

## Statistical Analysis Plan

### 2.6 Timing of Analysis

Data analyses will be performed when all subjects have either completed 5-year follow-up or have withdrawn from the study. In addition, study progress and data may be summarized and reported as needed.

### 2.7 Subgroups for Analysis

No subgroup analyses are planned for this clinical investigation.

### 2.8 Handling of Missing Data

There is no plan to impute missing data for this clinical study. All analyses will be performed on available data.

### 2.9 Adjustments for Covariates

Unless otherwise specified, no adjustments for covariates will be made for any of the variables in the analyses.

### 2.10 Sensitivity Analysis

If site-reported valve-related deaths include deaths that are also COVID-19 related, a sensitivity analysis of the primary safety endpoint will be performed with such deaths censored at the time of the event.

## 3.0 DESCRIPTIVE ENDPOINTS AND ADDITIONAL DATA

### 3.1 Baseline and Demographic Characteristics

The following baseline and demographic variables will be summarized for the subjects enrolled: age, gender, height, weight, BMI, cardiac disease history, arrhythmia history, indication for aortic replacement, cardiac medication, implant procedural characteristics, etc.

### 3.2 Adverse Events

All of the adverse device effects, serious adverse device effects will be summarized for all subjects who enrolled in this trial in terms the number of events, the percentage of subjects with events.

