7.3 Adverse Event and Device Deficiency/Device Malfunction Reporting

7.3.1 Adverse Event Reporting

Safety surveillance and reporting starts as soon as the subject is enrolled in the clinical investigation. Adverse events will not be collected for screen failure subjects. Safety surveillance and reporting will continue until sites perform the last follow-up visit, the subject is deceased, the subject concludes participation in the clinical investigation, or the subject withdraws from the clinical investigation. Sites should update additional information regarding an adverse event on the appropriate CRF.

Unchanged, chronic, non-worsening or pre-existing conditions are not AEs and should not be reported.

For the purpose of this trial, the following adverse event types will be reported:

- Adverse events considered related to the implanted Regent MHV
- All serious adverse events

Clinical Investigation Plan

In addition, the following endpoint-related adverse events meeting the Akins²⁵ criteria defined in Appendix II will be reported regardless of seriousness or relatedness:

- Death – all-cause and valve-related mortality
- Reinterventions of the replaced valve
- Major bleeding
- Thromboembolism
- Valve thrombosis
- Endocarditis (operated valve)
- Major paravalvular leak

The Investigator will assess the events for relationship to the device and relationship to the procedure.

The Sponsor will provide an offline form to allow the Investigator to report SAEs in the event the entry cannot be made in the EDC. This does not replace the EDC reporting system. Sites must still enter all information in the EDC system as soon as feasible.

SAE Reporting

The Investigator must report all SAEs to the Sponsor as soon as possible but no later than outlined below.

Clinical Site	Reporting timelines
All Sites	Investigators must report SAEs to the Sponsor no later than 24 hours from the day the site personnel became aware of the event or as per the investigative site's local requirements, if the requirement is more stringent than those outlined.

Sites must record the date the site staff became aware that the event met the criteria of an SAE in the source document. The Investigator will report the SAE to the local IRB/EC according to the institution's IRB/EC reporting requirements.

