15.2 Foreseeable Adverse Events and Anticipated Adverse Device Effects

Risks associated with the specified device and procedure are bleeding, hemolysis, endocarditis, infections, thrombus, or thromboembolism, valve dehiscence, unacceptable hemodynamic performance (including: elevated pressure gradients, prosthesis patient mismatch or transvalvular regurgitation), paravalvular leak, hemorrhagic complications secondary to anticoagulation therapy, prosthetic failure (including: pannus ingrowth (NSVD), leaflet fracture/ escape/ split/ dislodgement, and entrapped leaflet/ stuck valve/ leaflet immobility, thrombocytopenia, heart block requiring pacemaker implant, adjacent cardiac structure interference, stroke, heart failure, myocardial infarction, or death as described in the IFU. Any of these complications may require reoperation or explantation of the device. There may be risks related to the device under investigation that are unknown at present. Likewise, the exact frequency of the risk may be unknown.

15.3 Residual Risks Associated with the Device Under Investigation, as Identified in the Risk Management Report / Risk Analysis Report

Risk analysis of the Regent MHV device has been performed in accordance with the Risk Analysis Plan [REDACTED] and Design Failure Mode Effect Analysis [REDACTED] to systematically identify potential hazards associated with the design and use of this device. Based upon bench testing and prior Abbott-sponsored clinical study data, all risks have been identified and mitigated as far as possible through application of appropriate controls and inspections and determined to be within acceptable levels.

Residual risks are likewise disclosed in the IFU in the form of clear instructions of what actions to take or to avoid, to avoid a hazardous situation of harm from occurring (contra-indications, warnings, and precautions). The anticipated AEs disclosed in the IFU provide further information to enable the user, and potentially the subject, to make an informed decision that weighs the residual risk against the benefit of using the device.

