APPENDIX II: DEFINITIONS

The following definitions for primary and descriptive endpoint events will be used in this investigation. These definitions are taken from the Akins *et al.*²⁵ guidelines for adverse event reporting after cardiac valve interventions referenced in ISO 5910:2018 “Cardiovascular implants and extracorporeal systems—Cardiac valve repair devices.” Note that the Akins *et al.* definition of embolism is limited to thromboembolism, which is the term used in the text of the CIP. Similarly, the Akins *et al.* definition of a bleeding event is limited to major bleeding and this terminology is used in the CIP text.

All-cause Mortality: All-cause mortality includes all deaths from any cause after a valve intervention.

Embolism: Embolism is any embolic event that occurs in the absence of infection after the immediate perioperative period. Embolism may be manifested by a neurologic event or a noncerebral embolic event. A neurologic event includes any central, new neurologic deficit, whether temporary or permanent and whether focal or global, that occurs after the patient emerges from anesthesia. A noncerebral embolic event is an embolus documented operatively, at autopsy, or clinically that produces signs or symptoms attributable to complete or partial obstruction of a peripheral artery. Intraoperative myocardial infarctions are not counted. Postoperative myocardial infarction is also not counted unless the infarction is caused by a coronary embolus (as detected by operation, autopsy, or clinical imaging). Emboli consisting of non-thrombotic material (e.g., atherosclerosis, myxoma) are not counted.

Bleeding Event: A bleeding event is any episode of major internal or external bleeding that causes death, hospitalization, or permanent injury (e.g., vision loss) or necessitates transfusion. Major bleeding unexpectedly associated with minor trauma should be reported as a bleeding event, but bleeding associated with major trauma or a major operation should not. Bleeding events are reported for all patients regardless of whether they are taking anticoagulants or antiplatelet drugs. Although total bleeding events must be reported, bleeding events can also be reported separately for those who are taking anticoagulants or antiplatelet agents and those who are not.

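### SAP 3.2 summarizes only device effects, so non-fatal SAEs not attributed to the valve and outside the seven SAP 3.5 event types have no readable summary, and procedure relationship is not analysed

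*SAP*

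**What the plan says.** Protocol 7.3.1 sets out three groups of events that sites must report:

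- "Adverse events considered related to the implanted Regent MHV";
- "All serious adverse events", with no condition on attribution;
- seven endpoint event types, which "will be reported regardless of seriousness or relatedness": death, reintervention on the replaced valve, major bleeding, thromboembolism, valve thrombosis, operated-valve endocarditis and major paravalvular leak.

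The same section asks for two separate judgments: "The Investigator will assess the events for relationship to the device and relationship to the procedure". Protocol 7.2 makes the device judgment the investigator's, on the test of a reasonable possibility that the device caused or contributed to the event.

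SAP 3.2 is the only SAP section headed as adverse-event analysis. It reads: "All of the adverse device effects, serious adverse device effects will be summarized" for all enrolled subjects, as a number of events and a percentage of subjects. Two other readable SAP sections touch adverse events outside the primary endpoints. SAP 3.5 gives annualized rates of the seven endpoint types, and SAP 3.3 lists deaths among the reasons for early termination.

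Two protocol passages bear on what falls between these. Section 15.2 gives one combined list of foreseeable harms that opens "Risks associated with the specified device and procedure are bleeding, hemolysis, endocarditis, infections, thrombus, or thromboembolism" and goes on to include heart block needing a pacemaker, heart failure and myocardial infarction. Appendix II says of the major-bleeding endpoint that "bleeding associated with major trauma or a major operation should not" be reported as a bleeding event.

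**The concern.** The data collection is wider than the analysis. Sites report every SAE to the sponsor within 24 hours and the investigator attributes it twice, yet the stated adverse-event summary keeps only what was called a device effect. For an SAE outside the seven SAP 3.5 types, one investigator judgment then decides whether it appears in any readable table. The readable text describes no independent adjudication of that judgment.

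The study exists to confirm safety in a population in which the valve has not been studied prospectively (Protocol 1.1.1). The protocol treats procedural harm as relevant: sections 4.1 and 8.2.1 justify the primary safety endpoint partly by its correlation with severe events related to the device and to the procedure. In a single-arm study with no comparator, a full SAE listing by attribution is what would let a reader, including the NMPA, see how the device judgments were made. If an event is under-attributed, the present rule removes it from view.

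**Working it through.** No arithmetic applies, because SAP 3.2 states no rate or count. The check sets each category of event collected under Protocol 7.3.1 against each readable SAP summary and the Appendix II definitions.

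| Event collected | Readable summary |
|---|---|
| Device-related AE or SAE | SAP 3.2 |
| Death from any cause, whatever the attribution | SAP 3.5 (all-cause mortality) and SAP 3.3 |
| Reintervention on the replaced valve, whatever the attribution | SAP 3.5 |
| Major bleeding, thromboembolism, valve thrombosis, endocarditis or major paravalvular leak meeting the endpoint definition, whatever the attribution | SAP 3.5 |
| Non-fatal SAE outside the seven types, not attributed to the device | None |
| Relationship to the procedure, for any event | None |

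Two cases show how the fifth row arises.

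1. *Heart block with a pacemaker, judged procedure-related and not device-related.* Where it meets the SAE definition in Protocol 7.1.2, it is reported. It is not a device effect, so SAP 3.2 omits it. It is not among the seven types, so SAP 3.5 omits it. The subject survives, so SAP 3.3 omits it.

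2. *Reopening for bleeding after the index operation, with the valve untouched, judged not device-related.* SAP 3.2 omits it. Appendix II keeps bleeding associated with a major operation out of major bleeding, so that rate omits it. Appendix II defines reintervention as a procedure that repairs, alters or replaces the prosthesis, so that rate omits it too. If the subject survives, no readable summary is left.

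Embolism in the immediate perioperative period is a partial case. The opening of the Appendix II definition excludes it, but the neurologic-event sentence counts deficits once the patient emerges from anesthesia. Some perioperative events are therefore counted and others are not.

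The 15.2 harms do not all belong in the gap. Valve dehiscence, pannus or leaflet failure, haemodynamic failure or mismatch, and hemolysis are largely valve problems. They would normally be judged device-related and enter SAP 3.2, and any that led to reintervention or death would also enter SAP 3.5. The realistic remainder is mainly non-fatal heart block, myocardial infarction, heart failure, non-valve infection, thrombocytopenia and perioperative bleeding.

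**The case against.** The strongest reply has four parts.

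*The important events are already covered.* SAP 3.5 reports seven types with no device-relatedness condition. This stands, and it rules out the stronger inference a reader might draw from SAP 3.2 alone, that every SAE not attributed to the valve disappears from the safety tables. Deaths, reinterventions and the five morbidity types are visible whatever the investigator decides.

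*A device-focused table fits a device-focused objective.* The objective in Protocol 2.1 and SAP 1.2 is the safety and performance of the valve, and section 15.2 is a risk disclosure, not an aim. This stands too: the plan does not promise to confirm procedural safety, and the point should not be argued as though it did. It remains that the protocol collects a procedure-relationship assessment that no readable analysis uses.

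*The text may be broader than it looks.* SAP 3.2 does not say that nothing else will be tabulated. Adverse device effect is not defined in the readable text, and the heading of Protocol 15.2 places foreseeable events and device effects over one list that includes heart block. SAP 7.0 is redacted or not shown and could hold table shells for all SAEs, and the content of Protocol Appendix V is likewise not readable. None of this can be excluded, and it lowers confidence. It does not remove the point, because if a wider meaning was intended, the only adverse-event rule rests on an undefined term.

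*The information reaches others anyway.* SAEs go to the sponsor and, by local rules, to ethics committees, and Protocol 8.8 puts follow-up data into annual reports to the NMPA. But 8.8 names no SAE table, and the sponsor's 7- and 15-day reports to authorities in Protocol 7.3.3 are themselves tied to device-related events.

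A reader might also infer that attribution error can only make the valve look safer. The documents do not support that. Calling an unrelated event device-related raises the SAP 3.2 count, and the reasonable-possibility test in Protocol 7.2 is broad. The supportable statement is that under-attribution takes an event outside the seven types out of sight.

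**Conclusion.** The point holds in a limited form and should be corrected. Under the readable text, a non-fatal SAE that is not attributed to the valve and is not one of the seven SAP 3.5 types has no summary, and one of the two attribution judgments collected is never analysed.

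The size can be stated by category but not by count. The readable documents give no SAE rate for the 200 implanted subjects, so any figure for subjects affected would be an assumption, and the point does not depend on one. The consequence is incomplete safety reporting: neither primary endpoint changes, and Protocol 8.6 plans no formal hypothesis test that could be affected.

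Confidence is moderate. The conclusion assumes that adverse device effect in SAP 3.2 means an event judged related to the device, and that the unreadable SAP 7.0 holds no table of all SAEs.

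**What to change.** Amend SAP 3.2 to:

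- define adverse device effect and serious adverse device effect, and say whether procedure-related events are included;
- summarize all SAEs, as number of events and percentage of subjects, by event type, by relationship to the device and by relationship to the procedure;
- keep the present device-effect tables as a subset of that summary.

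Grouping by the harms named in Protocol 15.2, and splitting early from late events, would help a reader but are optional. If SAP 7.0 already holds such shells, SAP 3.2 need only define the term and refer to them.

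The cost is SAP wording and a few extra tables from data the protocol already collects. No new data collection or change to the primary analyses is needed. The reported safety burden may look less favourable, because events unrelated to the valve will be shown; presenting them by attribution keeps that readable.

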5.4 Subject Enrollment

A patient is considered enrolled in the clinical investigation from the moment the patient provides written informed consent.

Clinical Investigation Plan

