5.5 Subject Withdrawal and Discontinuation

Each subject enrolled shall remain in the clinical investigation until completion of the required follow-up period; however, a subject's participation in any clinical investigation is voluntary, and the subject has the right to withdraw at any time without penalty or loss of benefit. Conceivable reasons for discontinuation may include, but not be limited to, the following:

- Subject death
- Subject did not undergo the Regent MHV implant surgery within 60 days of enrollment
- Subject had an unsuccessful implant of the Regent MHV
- Subject voluntary withdrawal
- Subject lost-to follow-up as described below
- Subject's follow-up is terminated according to Section 3.3

Note: Subjects who undergo a surgical reintervention following the implant of the Regent MHV will not be withdrawn from the study as a consequence of the reintervention. Such subjects will continue follow-up until completing their last scheduled study visit unless withdrawn from the study for another reason.

Sites must notify the Sponsor of the reason(s) for subject discontinuation. Investigators must also report this to their respective IRB/EC as defined by their institution's procedure(s).

No additional follow-up is required or data recorded from subjects once withdrawn from the clinical investigation, except for the status (deceased/alive).

However, if a subject withdraws from the investigation due to problems related to the safety or performance of the device under observation, the Investigator shall ask for the subject's permission to follow his/her status/condition outside of the clinical investigation.

Lost-to-Follow-up

If the subject misses two consecutive scheduled follow-up time points and the attempts at contacting the subject detailed below are unsuccessful, then the subject is considered lost-to-follow-up. Site personnel shall make all reasonable efforts to locate and communicate with the subject (and document these efforts in the source documents), including the following, at each contact time point:

- A minimum of two telephone calls on different days over the specified follow-up windows to contact the subject should be recorded in the source documentation, including date, time and initials of site personnel trying to make contact.
- If these attempts are unsuccessful, the site should send a letter (certified if applicable) to the subject.

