5.6 Number of Subjects

The clinical investigation will enroll 200 eligible implanted subjects. No site may enroll more than 40% of the total subjects. Allowing for subjects who provide written informed consent but are withdrawn without undergoing a Regent MHV implant, RC-PMCF study enrollment is expected to be less than 250 subjects.

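### SAP 3.2 puts device effects over all enrolled subjects with no time at risk: read literally the percentage is diluted, and effects outside SAP 3.5 get no visible valve-year rate

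*SAP*

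**What the plan says.** Under SAP 3.2, adverse device effects and serious adverse device effects are to be "summarized for all subjects who enrolled in this trial in terms the number of events, the percentage of subjects with events". No time at risk enters the summary.

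Three other places bear on who is in that denominator:

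- Protocol 5.4: "A patient is considered enrolled in the clinical investigation from the moment the patient provides written informed consent".
- SAP 1.3: subjects who enroll but do not receive the valve within 60 days "will be withdrawn from the study and will not contribute to the study sample size".
- Protocol 5.6: the target is 200 implanted subjects. Allowing for those who consent but are never implanted, "RC-PMCF study enrollment is expected to be less than 250 subjects".

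On the numerator, Protocol 7.3.1 lists the device-related reportable events as "Adverse events considered related to the implanted Regent MHV", and it collects no adverse events for screen failures. The only analysis population that the visible SAP names is under the heading "2.1.1 Implant Population". Its definition is not readable, and SAP 3.2 does not refer to it.

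SAP 3.5 reports seven outcomes per valve-year: all-cause mortality, reintervention, major bleeding, thromboembolism, valve thrombosis, endocarditis and major paravalvular leak. Protocol 15.2 names further foreseeable risks, among them hemolysis, pannus ingrowth and a stuck leaflet. Under Protocol 5.5 and 7.3.1, event recording ends at withdrawal and only vital status may follow. SAP 2.8 plans no imputation.

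**The concern.** There are two separate weaknesses.

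The first is the denominator. A subject who consents and is never implanted can add to the bottom of the fraction but not to the top. If SAP 3.2 is programmed as worded, the percentage is a mixture over patients with and without the device, and it reads lower than the risk in implanted patients.

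The second is exposure. A subject who withdraws event-free in year 1 weighs the same as one observed event-free for five years. For the seven SAP 3.5 outcomes a valve-year rate is also planned, so this does little harm. It matters for device effects that are non-fatal, not reintervened on and outside that list, such as hemolysis or pannus managed conservatively and judged device-related. For these, the crude percentage is the only relative measure in the visible text, and it cannot be set beside the SAP 3.5 rates in the same report.

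Both weaknesses push the figure down, in a study whose purpose is to confirm safety.

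**Working it through.** The plan gives no figure to reproduce here. SAP 3.2 contains no number, and the sample-size justification is redacted.

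**Inputs.** From the documents: 200 implanted (SAP 2.4), fewer than 250 enrolled (Protocol 5.6), 5 years of follow-up (SAP 1.3). Assumed, because the visible text gives no value: the number enrolled N within that bound, a true 5-year risk of 5% for illustration, and constant loss hazards *l* of 0, 0.02 and 0.05 per year.

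**Step 1: denominator alone.** Relative shortfall = 1 − 200/N.

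| N enrolled | Never implanted | Shortfall | 10 affected subjects shown as |
|---|---|---|---|
| 200 | 0 | 0% | 5.00% |
| 210 | 10 | 4.8% | 4.76% |
| 220 | 20 | 9.1% | 4.55% |
| 249 | 49 | 19.7% | 4.02% |

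**Step 2: incomplete follow-up alone.** The event hazard is h = −ln(1 − 0.05)/5 = 0.01026 per year. The expected number of affected subjects among 200 implanted is 200 × h/(h + *l*) × (1 − exp(−5(h + *l*))). Valve-years are 200 × (1 − exp(−5*l*))/*l*, or 1,000 with no loss.

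| *l* per year | Lost by 5 years | Affected subjects seen | Percentage of 200 | Shortfall | Valve-years | Per 100 valve-years |
|---|---|---|---|---|---|---|
| 0 | 0% | 10.00 | 5.00% | 0% | 1,000 | 1.00 |
| 0.02 | 9.5% | 9.52 | 4.76% | 4.8% | 952 | 1.00 |
| 0.05 | 22.1% | 8.86 | 4.43% | 11.4% | 885 | 1.00 |

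For *l* = 0.02: 200 × (0.01026/0.03026) × (1 − exp(−0.1513)) = 9.52. Dropout alone therefore hides 10 − 9.52 = 0.48 to 10 − 8.86 = 1.14 subjects. The valve-year rate does not move, but that stability follows from the constant-hazard assumption.

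**Step 3: set against sampling error.** The exact 95% interval for 10/200 is 2.4% to 9.0%. Every shifted percentage above lies inside it, though all shifts go the same way.

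**The case against.** The strongest objection is that the documents use the word enrolled in two ways. SAP 2.4, Protocol 5.6 and Protocol 8.3 speak of enrolling 200 implanted subjects. SAP 1.3 does much the same before it turns to subjects who enroll and are not implanted. SAP 3.1, directly before the sentence at issue, summarizes implant-procedure data for enrolled subjects, which only operated subjects can have. On that reading the dilution is nil. This stands, and it makes the first weakness conditional. It does not remove it: the one explicit definition (Protocol 5.4) and the withdrawal sentence in SAP 1.3 point to consent, and no visible text overrides the wording of SAP 3.2.

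Second, the Implant Population text, Protocol 8.1 and the SAP appendix are redacted or unreadable, so a different denominator or an exposure-based table may be specified there. This also stands. The point concerns only the text that can be read.

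Third, SAP 3.5 already covers the main time-dependent valve events. Reintervention as defined in Protocol Appendix II takes in any surgical or catheter procedure on the valve, so treated pannus or a treated stuck leaflet has a rate. A reader might infer that device effects in general lack exposure adjustment. The documents do not support that. The gap is a residual class whose frequency is not stated.

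Fourth, counts and percentages are an ordinary descriptive summary. SAP 3.2 attaches no criterion to them, the counts do not depend on the denominator, and SAP 3.3 shows losses by visit. That is fair, and it limits the weight of the point. The loss table does not correct the percentage, however. Finally, the present wording has one merit: it keeps device effects in subjects with an unsuccessful implant, and a change of denominator must not lose them.

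**Conclusion.** The point holds as a minor one. Read literally, SAP 3.2 understates the percentage of implanted patients with a device effect by 1 − 200/N: 9% at 220 enrolled and just under 20% at the bound. The understatement is zero if enrolled was meant as implanted. On either reading, effects outside SAP 3.5 have no time-at-risk measure in the visible text. With an assumed 2% to 5% annual loss and constant hazards, their percentage is about 5% to 11% low in relative terms, and with complete follow-up it is not low at all. If such effects cluster early after implant, dropout matters less.

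A reader might add the two parts and speak of a shortfall near 29%: 1 − (8.86/249)/0.05 = 0.288. That joins the largest permitted enrollment to the heaviest loss assumed here, and the documents support neither as an expectation. Protocol 3.2 aims at high follow-up compliance. Nor does the point reach the study's conclusions, since no primary endpoint, acceptance criterion or SAP 3.5 rate changes.

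**What to change.** In SAP 3.2:

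1. Make implanted subjects the denominator for adverse device effects and serious adverse device effects, and keep the counts and percentages.
2. List separately any device effect in a subject with an unsuccessful implant, which Protocol 5.5 gives as a reason for discontinuation.
3. Add events per 100 valve-years with an exact Poisson 95% interval, using the valve-years already needed for SAP 3.5.

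A separate percentage for events within 30 days of implant would help if effects come early, but it is optional and not part of the correction.

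The cost is one or two SAP sentences and an extra table column or two, with no protocol change. The rates will be imprecise for sparse categories: at 1,000 valve-years, 0 events gives an upper limit of 0.37 per 100, and 3 events gives 0.30 (0.06 to 0.88). The Poisson interval also treats repeat events in one subject as independent, which a table footnote should say.
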